7.2 Detection of Bias

Participants will be assigned to treatment by a randomization schedule developed and maintained by an independent statistician. The treatment in this study will be blinded to the subjects, investigators, any individual conducting the study (e.g., nursing and pharmacy staff) and clinical study personnel.

Where required, safety personnel and/or investigator may be unblinded to a particular subject's treatment assignment. Data collected after unblinding will be noted.

7.3 Outliers

No formal outlier tests are planned. Values that are outside the pre-defined acceptable clinical range would be queried and excluded if necessary prior to database lock.

7.4 Testing/Validation Plan

All statistical analyses will be programmed using SAS® software version 9.4, or later or equivalent. Graphic displays may be produced using R, version 3.0.0, or later. Standard macros will be used in programming when possible. Testing and validation plans for all programs will be developed in accordance with contract research organization guidelines and will include independent programming of tables and analyses.

Statistical Analysis Plan (SAP) for Clinical Study AP-017

8. STATISTICAL METHODS OF ANALYSIS

8.1 General Principles

Data will be summarized by each treatment arm and by pooled Control and Ampion arms. Descriptive statistics on continuous variables will include mean, standard deviation, median, 25th, and 75th percentiles, and range. Change from baseline will include a 95% confidence interval. Categorical variables will be summarized using frequency counts and percentages. Data listings of individual subject's data will be provided. No statistical testing will be performed.

8.2 Subject Accountability

The number of subjects who are randomized, receive study drug, and complete the study will be summarized. The number of subjects included in the safety and ITT analysis sets will be included in the table. Attendance at each assessment (see Schedule of Assessments), including missed visits, discontinuations, lost to follow-up, and percentage accountability will be summarized. A list of subjects who withdraw early will be provided. It will include the reason and timing of the withdrawal. Similarly, the reason any subject is excluded from an analysis set will also be provided. In addition, significant known protocol deviations will be noted for individual subjects; a summary table may also be provided.

8.3 Demographic and Baseline Characteristics

Age, gender, race, height and weight, and comorbidities will be summarized by treatment arm for all subjects receiving study drug, using descriptive statistics.

8.4 Safety Analyses

The safety profile will be based on adverse events, vital signs, blood oxygen saturation level, clinical laboratory measurements, and concomitant medications. All treated subjects will be included in the safety analyses.

8.4.1 Adverse events

Adverse events will be grouped by system organ class and by preferred term within system organ class according to the latest version of the MedDRA coding dictionary. The number of subjects reporting at least one adverse event and each adverse event will be summarized treatment group. Tables and/or narratives of any on-study death, serious or significant adverse events, including early withdrawals because of adverse events, will be provided should they occur.

The analysis of incidence of adverse events (AEs) and serious adverse events (SAEs) from baseline to Day 60 are described below.

The hypotheses to be tested are:

$$H_0: \pi_A = \pi_S \text{ versus } H_A: \pi_A \neq \pi_S$$

Where π_A and π_S represent the adverse event rates for Ampion and Placebo during the first 60 days after randomization.

The difference between Ampion and Placebo will be tested using the appropriate chi-square test or Fisher's exact test utilizing PROC FREQ with the EXACT option, if necessary.

Statistical Analysis Plan (SAP) for Clinical Study AP-017

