8.2 Definition of a Serious Adverse Event

A Serious Adverse Event (SAE) is any untoward medical occurrence that occurs at any dose that:

- Results in death
- Is life-threatening (patient is at immediate risk of death from the event as it occurred)
- Requires prolongation of existing hospitalization
- Results in persistent or significant disability/incapacity
- Results in any congenital anomaly/birth defect

Important medical events that may not result in death, are not life-threatening, or do not require hospitalization may be considered SAEs when, based on appropriate medical judgment, they may jeopardize the patient and may require medical or surgical intervention to prevent one of the outcomes listed in this definition. Examples of such events include allergic bronchospasm requiring intensive treatment or blood dyscrasias or convulsions that do not result in in-patient hospitalization.

Hospitalizations for elective surgery or other medical procedures that are not related to a treatment-emergent AE are not considered SAEs.

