2.4 Sample Size

The trial is designed to enroll up to approximately 200 patients across two treatment arms (active or control), with 100 subjects per arm, randomized 1:1 using a random allocation sequence stratified by COVID-19 disease severity (severe or critical). An interim analysis of the data is planned after 30 subjects (approximately n=15 subjects per arm) to evaluate the relative effect. At the interim analysis, the sample size may be re-estimated to determine the additional number of patients required for adequate power to meet the chosen effect size for the primary endpoint.

The number of participants is selected based on the effects observed for the primary endpoint, prevention of need for mechanical ventilation or death prior to day 28. A study recently reported in Lancet Respiratory Medicine with 243 hospitalized patients receiving the placebo for COVID-19 found 22% did not achieve day 28 ventilation-free survival (Lancet Respir Med 2021; [https://doi.org/10.1016/S2213-2600\(21\)00494-X](https://doi.org/10.1016/S2213-2600(21)00494-X)). In the AP-014 study, a lower rate (8%) was observed for subjects receiving inhaled Ampion. Assuming the same proportions (8% for Ampion and 22% for control) by Day 28, with 100 subjects per group, a two-sided 5% significance level, and using a z-test with unpooled variances, then under binomial enumeration the power to detect this difference is about 81.3%.

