3. STUDY ENDPOINTS AND ANALYSES

Statistical Analysis Plan (SAP) for Clinical Study AP-017

3.1 Primary Endpoint:

The primary endpoint assesses the effect of Ampion compared to placebo on prevention of need for mechanical ventilation or death prior to day 28. This is measured as the occurrence of mechanical ventilation or death by Day 28.

Let π_A and π_S represent the rate of this outcome for Ampion and control during the first 28 days after randomization. Then it is desired to demonstrate that the mechanical ventilation and death rate for Ampion is different than the corresponding rate for the control. Formally, this is presented as:

$$H_0: \pi_A = \pi_S \text{ versus } H_A: \pi_A \neq \pi_S$$

This will be tested utilizing the appropriate chi-square test or Fisher's exact test utilizing PROC FREQ with the EXACT option, if necessary.

Also, the median time to mechanical ventilation or death will be tested for difference between the two groups via the log-rank test. The test will be performed using PROC LIFETEST. The time to event distributions in each group will be estimated using the method of Kaplan and Meier.

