4. DEFINITIONS

4.1 Adverse Event:

An adverse event (AE) is defined as any undesired medical occurrence in a patient or clinical investigation patient receiving a pharmaceutical product and which does not necessarily have a causal relationship with this treatment. An AE can therefore be any unfavorable sign and unintended sign (including an abnormal laboratory finding), symptom, or disease temporarily associated with the use of a study drug, whether or not related to the study drug.

AEs will be graded for severity using the following categories. Missing grade will be assigned a grade of 3 (severe) in tabulations.

- **Grade 1 (MILD):** The symptom is barely noticeable to the study patient and does not influence performance or functioning. Concomitant medication is not ordinarily indicated for relief of mild AEs.
- **Grade 2 (MODERATE):** The symptom is of sufficient severity to make the study patient uncomfortable and to influence performance of daily activities. Concomitant medication may be indicated for relief of moderate AEs.
- **Grade 3 (SEVERE):** The symptom causes severe discomfort, sometimes of such severity that the study patient cannot continue in the study. Daily activities are significantly impaired or prevented by the symptom. Concomitant medication may be indicated for relief of severe AEs.

Relationship to study drug will be coded using the following categories. Missing relatedness will be assigned to related in tabulations.

- **Unrelated:** The adverse event is unlikely to have been caused by study drug.
- **Possibly related:** It is unclear whether the adverse event may have been caused by study drug.
- **Related:** The adverse event is likely to have been caused by study drug.

4.2 Serious Adverse Event:

A serious adverse event (SAE) is defined as an adverse event that

- Results in death
- Is life-threatening (patient is at immediate risk of death from the event as it occurred)

Statistical Analysis Plan (SAP) for Clinical Study AP-017

- Requires prolongation of existing hospitalization
- Results in persistent or significant disability/incapacity
- Results in a congenital anomaly/birth defect

4.3 Treatment-Emergent AE:

A treatment-emergent AE (TEAE) is any AE that begins or increases in severity after the initial dose of study drug.

4.4 Age:

Subject's age is defined as its integer value in years at enrollment.

4.5 Baseline:

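### The only tested SAE comparison overlaps the primary endpoint, so if Ampion works as planned it loses sensitivity to other serious harm and can even point the wrong way

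*SAP*

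**What the plan says.** The primary endpoint (SAP 3.1) is a composite: "This is measured as the occurrence of mechanical ventilation or death by Day 28". SAP 2.4 plans for a large effect on it: "Assuming the same proportions (8% for Ampion and 22% for control) by Day 28, with 100 subjects per group, a two-sided 5% significance level".

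The SAE criteria in SAP 4.2 and protocol 8.2 include "Results in death", "Is life-threatening (patient is at immediate risk of death from the event as it occurred" and "Requires prolongation of existing hospitalization". Neither document exempts primary-endpoint events or disease progression. Protocol 8.3 requires deaths during the study period to be reported in all cases.

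For the analysis, SAP 8.4.1 says "The analysis of incidence of adverse events (AEs) and serious adverse events (SAEs) from baseline to Day 60 are described below" and follows with a single hypothesis of equal event rates over 60 days, tested by chi-square or Fisher's exact test. Protocol 9.4.2 puts AE/SAE incidence first in its ordered list of secondary endpoints. SAP 8.1 says that no testing will be done, which does not fit with 8.4.1. The point below holds either way, because the quantity compared is the same.

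The planned safety tables, shown by arm, include treatment-emergent SAEs by system organ class and preferred term (Table 10.3.4). SAP 8.4.1 also provides for tables and/or narratives of deaths and serious events. No table or test gives a patient-level count of SAEs other than endpoint events.

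**The concern.** The SAE comparison is read as a statement about harm, but here it contains much of the efficacy outcome. A drug that prevents death and ventilation lowers its own SAE rate. If the same drug causes other serious events, the two effects partly cancel in the total. Safety is a stated secondary objective (SAP 2.2), and this is the only SAE quantity formally compared. A report could therefore say that serious events were similar, or fewer, on Ampion while serious harm outside the endpoint was higher.

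**Working it through.** **Inputs from the documents.** Endpoint rates of 8% and 22%, 100 per arm and two-sided 5% (SAP 2.4). Chi-square test (SAP 8.4.1 allows chi-square or Fisher).

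**Assumptions.** The rate of other SAEs, *q*, is not in the documents and is varied. Every endpoint event is taken to be an SAE, and the two event types are independent. Both are relaxed below.

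**The plan's own figure.** Enumerating both binomials at n = 100 per arm with the unpooled z-test gives 81.28% power for 8% against 22%. The stated 81.3% reproduces.

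**Any-SAE rate.** With endpoint rate *e*, any-SAE = 1 − (1 − *e*)(1 − *q*). For *q* of 10% on placebo and 20% on Ampion:
- Placebo: 1 − 0.78 × 0.90 = 29.8%
- Ampion: 1 − 0.92 × 0.80 = 26.4%

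**Chance of showing harm.** This is the exact probability that the chi-square test rejects with Ampion higher:

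| Endpoint, Ampion / placebo | Other SAEs, Ampion / placebo | Any SAE, Ampion / placebo | On all SAEs | On non-endpoint SAEs |
|---|---|---|---|---|
| 8% / 22% | 10% / 5% | 17.2% / 25.9% | <0.1% | 27% |
| 8% / 22% | 20% / 10% | 26.4% / 29.8% | 0.6% | 52% |
| 8% / 22% | 25% / 10% | 31.0% / 29.8% | 3.9% | 82% |
| 8% / 22% | 26.4% / 13.2% | 32.3% / 32.3% | 2.5% | 66% |
| 8% / 22% | 40% / 20% | 44.8% / 37.6% | 18% | 88% |
| 8% / 22% | 60% / 30% | 63.2% / 45.4% | 73% | 99% |
| 15% / 22% | 20% / 10% | 32.0% / 29.8% | 5% | 52% |
| 22% / 22% | 20% / 10% | 37.6% / 29.8% | 21% | 52% |

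In the first row the all-SAE test also has a 32% chance of declaring significantly fewer SAEs on Ampion.

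**Break-even for a doubling.** Setting 0.92(1 − 2*q*) = 0.78(1 − *q*) gives 0.14 = 1.06*q*, so *q* = 13.2%. Below that placebo rate the total favours Ampion, and above it the total points to harm.

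**Relaxing the assumptions, other SAEs 20% against 10%.**
- Only 80% of endpoint events are SAEs (6.4% and 17.6%): any-SAE is 25.1% Ampion and 25.8% placebo, with a 1.9% chance of showing harm. The break-even placebo rate falls to 10.7%.
- Endpoint and other SAEs never occur in the same patient, so the rates add: 28.0% Ampion and 32.0% placebo, 0.5%. The break-even becomes 14%.
- Fisher's test instead of chi-square, original assumptions: 0.4% on all SAEs and 44% on non-endpoint SAEs.

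**How much is due to efficacy.** The last table row has no efficacy effect, and the all-SAE test still has only 21% power against 52%. That part is ordinary dilution by events unrelated to the harm. The fall from 21% to 0.6% is due to the efficacy effect.

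**The case against.** A reader might infer that the plan has no other view of SAEs and would hide a doubling of serious harm. The documents do not support that. Table 10.3.4 shows SAEs by preferred term and arm, and narratives and listings are planned. The DSMB reviews SAEs (protocol 3.5), and protocol 6.1 suspends the study for certain related events. A cluster of one kind of event would appear in its own row. What stands is narrower: a patient may appear under several terms, so the rows cannot be summed to patients affected, and harm spread over many terms can look like noise in each. DSMB review does not supply a final comparison.

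A reader might also infer that every death and nearly every ventilation event is an SAE. That is too strong. The endpoint uses all randomized patients (SAP 5.1.2) but the SAP safety set only treated ones (5.1.1), so a death before dosing counts in one and not the other. No section names ventilation as an SAE. Patients on endotracheal ventilation may enrol (protocol 4.4), and the wording of protocol 3.3.1 could count them without any new event. Protocol 8.3 closes AE reporting at discharge, although other sections run to Day 60.

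Finally, the size rests on an assumed rate in a severe or critical population, where other SAEs may be common. At 20% doubling to 40% the total already points to harm. This limits the claim of reversal but not the loss of sensitivity, which appears in every scenario above. A separate test is not strong either (52% at 20% against 10%), which argues for an estimate with an interval.

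**Conclusion.** The concern holds in a limited form. The one tested SAE comparison includes deaths in treated patients and, by inference, probably most new ventilation events. If Ampion works as planned, that comparison becomes much less sensitive to other serious harm. It can favour Ampion while other SAEs double, but only with roughly the full 8% against 22% effect and an assumed placebo rate of other SAEs below about 13%. With a 15% against 22% effect, or with higher rates of other SAEs, the direction is right but power stays well below that of a separate count. The gap in the plan is a missing patient-level summary, not an absence of SAE reporting.

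**What to change.** Keep the all-SAE comparison. Add three pre-specified rows by arm to SAP 8.4.1 and the safety tables:
- Patients with at least one SAE other than an endpoint SAE, with risk difference and 95% CI.
- Deaths by recorded cause (protocol 5.2 already provides for cause to be documented).
- Patients with an SAE judged possibly related or related. Tables 10.3.3 and 10.3.6 cover related AEs but not related SAEs.

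Define an endpoint SAE before unblinding: an SAE with a fatal outcome, or one recorded as the event leading to new mechanical ventilation by Day 28. The definition is needed because SAEs are coded to preferred terms, not as death or ventilation. The second and third rows keep a drug-caused fatal SAE in view after the first row has excluded it. The safety conclusion should cite all the rows.

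The cost is a little more table work. Intubation dates, AE outcome, relatedness and cause of death are already collected. The documents do not show a field linking an SAE to intubation, so that link may need a short blinded review. Patients who die early have less time to have other SAEs, which a footnote should state.

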2.3 Previous Human Experience

Human serum albumin (HSA, 5%) is a human blood product approved by FDA for intravenous (IV) infusion to treat hypovolemia and other serious conditions, including ARDS (Polito 2013, Farag, 2016). Albumin and large molecules are removed to manufacture Ampion, the low molecular weight (< 5 kDa) ultrafiltrate of 5% HSA.

Ampion has been investigated for clinical use as an IV treatment compared to standard of care for adults with COVID-19 infection requiring supplemental oxygen in a Phase 1, randomized, open label study in 10 adults with severe COVID-19. The study met its primary endpoint for the safety and tolerability of IV Ampion treatment, with no remarkable difference in the incidence, frequency, and severity of adverse events between IV Ampion and standard of care. At hospital discharge, Ampion-treated patients showed greater clinical improvement than standard of care alone using the WHO ordinal scale and NEWS2 scale for clinical health.

Ampion is also in human clinical development for a separate inflammatory indication (arthritis). In that program more than 1,000 patients have been exposed to a localized 4cc injection of Ampion with no treatment-related adverse events.

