9.4.2 Secondary Endpoints

Secondary efficacy endpoints assess the effect of IV Ampion compared to SOC on the clinical outcomes for participants with COVID-19 on supplemental oxygen. The secondary endpoints will be tested in a hierarchical manner in the order presented, and thus no adjustment to the alpha level is necessary:

Objective	Endpoint
Secondary Endpoints	
Assess the effect of Ampion compared to placebo on safety	
Incidence of adverse events (AEs) and serious adverse events (SAEs) from baseline to Day 60.
Assess the effect of Ampion compared to placebo on clinical improvement	
Change in ordinal scale from baseline through Day 7.Change in ordinal scale from baseline to hospital discharge or day 14 (whichever occurs first).Change in ordinal scale from baseline to hospital discharge or day 28 (whichever occurs first).Change in NEWS2 score from baseline through Day 5.Change in NEWS2 score from baseline to hospital discharge.Modulation of cytokine levels from baseline to Day 5.
Assess the effect of Ampion compared to placebo on duration of respiratory failure to ventilator-free days.	
Percentage of participants who progress to respiratory failure (i.e., need for mechanical ventilation, ECMO, non-invasive ventilation) by Day 28.

Objective	Endpoint
Assess the effect of Ampion compared to placebo on intensive care	
Percentage of participants who require Intensive Care Unit (ICU) admission by Day 28.ICU-free days through Day 28.ICU LOS from ICU admission to discharge.
Assess the effect of Ampion compared to placebo on hospital stay	
Hospital length of stay (LOS) from admission to discharge.Hospital-free days through Day 28.
Assess the effect of Ampion compared to placebo on oxygen use	
Duration of oxygen use, blood oxygen saturation, and oxygen flow rate from baseline through Day 5.

The efficacy endpoints will be evaluated to estimate the treatment effect and use descriptive statistics including mean, standard deviation, percentages, minimum/maximum, and 95% confidence intervals. All endpoints will be tabulated and presented by treatment arm, cohort (severe and critical), and timepoint. Where appropriate, data will be tabulated and presented cumulatively across cohorts and/or timepoints.

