6. INTERIM ANALYSIS AND EARLY STOPPING GUIDELINES

6.1 Interim Analysis

This trial is designed to enroll up to approximately 200 subjects, randomized to active or control, following an equal allocation to treatment arms. An interim analysis of the data is planned after 30 subjects (approximately n=15 subjects per arm) to evaluate the relative treatment effect.

The interim analysis will be conducted on the primary and secondary endpoint data at an alpha level of 0.001 and thus the overall alpha level for the final test will be performed at approximately $\alpha=0.049$ instead of $\alpha=0.05$.

At the interim analysis, the sample size may be re-estimated to include additional subjects up to a total of 300 subjects to attain adequate power beyond the sample size of 200 originally calculated. This evaluation will be based on the methodology suggested by Gould et al. (Gould AL. Interim analyses for monitoring clinical trials that do not materially affect the type I error rate. Stat Med 1992; 11(1): 55-66) Let σ be the pooled rate of this study endpoint in the two arms, i.e. $\sigma=(p_{placebo}+p_{Ampion})/2$, where p is the incidence of the primary study endpoint in the respective groups. Let σ^* be the same value, but based on some assumed rates for these values from the beginning of the trial. Then the following sample size multiplier is determined:

$$f = [\sigma(1-\sigma)]/\sigma^*(1-\sigma^*)$$

If f is greater than 1, then the new sample size, n_1 , is determined as $f \times n$, where n is the original sample size (per group) of 100. If f is less than one, then the study will continue as originally envisioned.

The sponsor reserves the right to alter the final sample size if the assumptions of the rates of the primary endpoint are not satisfied at this interim analysis.

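### The SAP's only between-arm analysis of AEs and SAEs is a two-sided test of equal incidence; a risk difference with a 95% confidence interval should be added

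*SAP*

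**What the plan says.** Protocol 9.4.2 puts safety first in its ordered list of secondary endpoints, as "Incidence of adverse events (AEs) and serious adverse events (SAEs) from baseline to Day 60". It adds that binary outcomes will be compared by Fisher's exact test.

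SAP 8.4.1 carries this out. It sets a null hypothesis of equal event rates over 60 days against a two-sided alternative, and then says that "The difference between Ampion and Placebo will be tested using the appropriate chi-square test or Fisher's exact test". It states no risk difference or ratio, interval, upper limit or margin.

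The general rule in SAP 8.1 is that "Categorical variables will be summarized using frequency counts and percentages". That section attaches a 95% interval only to change from baseline. It also says that no tests will be carried out, and SAP 8.6.1 says something similar; both conflict with 8.4.1. The AE tables listed in the SAP (10.3.1 to 10.3.6) are incidence tables by arm.

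The trial is sized for the primary endpoint, "with 100 subjects per arm, randomized 1:1 using a random allocation sequence". SAP 6.1 allows re-estimation "up to a total of 300 subjects to attain adequate power beyond the sample size of 200 originally calculated". Neither document gives a power or a detectable difference for the safety comparison.

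**The concern.** With a test of equality, the result that favours the drug on safety is a failure to reject, and a smaller or less sensitive trial fails to reject more often. A p-value above 0.05 therefore does not separate a trial that has ruled out an important excess from one that could not have seen it. An interval for the difference does, because its upper limit is the largest excess still compatible with the data. The SAP plans the p-value and omits the interval. At stake is how informative the between-arm safety comparison will be in a population where SAEs include deaths and life-threatening events.

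**Working it through.** **1. Check of the method on the plan's own figure.** SAP 2.4 gives 8% versus 22%, 100 per arm, two-sided 5%, an unpooled z-test and binomial enumeration, with stated power of 81.3%. Power is the sum, over all pairs (a, b) that reject, of Bin(a; 100, 0.08) × Bin(b; 100, 0.22). This gives 81.28%, so the stated figure is reproduced.

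**2. Inputs for the safety test.**
- n = 100 per arm (SAP 2.4), and 150 per arm at the maximum of 300 (SAP 6.1).
- Pearson chi-square or Fisher's exact test (SAP 8.4.1).
- Alpha 0.05 two-sided, assumed because none is stated for this test. Using the final levels of 0.049 (SAP 6.1) or 0.047 (Protocol 9.2.3) raises the miss rates by about 2 points at most.
- Placebo SAE rate: not given, so assumed over 5% to 50%. As context only, the planned control rate of ventilation or death is 22%.

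**3. Chance of missing a true 10-point excess.** Miss rate = 1 − Σ Bin(a; n, p+0.10) × Bin(b; n, p), summed over pairs with a > b that reject.

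| Placebo → Ampion | 100 per arm, chi-square / Fisher | 150 per arm, chi-square / Fisher |
|---|---|---|
| 5% → 15% | 32% / 41% | 16% / 20% |
| 10% → 20% | 48% / 56% | 31% / 37% |
| 20% → 30% | 63% / 69% | 48% / 53% |
| 30% → 40% | 68% / 74% | 56% / 61% |
| 40% → 50% | 69% / 74% | 57% / 61% |
| 50% → 60% | 69% / 74% | 57% / 61% |

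For 80% power against a 10-point excess, about 199, 294, 356 and 388 patients per arm would be needed at placebo rates of 10%, 20%, 30% and 40%.

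**4. What an interval would show.** Newcombe's upper limit is d + √[(u₁ − p₁)² + (p₂ − l₂)²], where u₁ is the upper Wilson limit for Ampion and l₂ the lower Wilson limit for placebo.
- *31 versus 20 of 100.* The pooled rate is 0.255, the standard error √(2 × 0.255 × 0.745/100) = 0.0616, and z = 0.11/0.0616 = 1.78. So p = 0.07 by chi-square, and 0.10 by Fisher. With u₁ = 0.4063 and l₂ = 0.1334, the upper limit is 0.11 + √(0.0963² + 0.0666²) = 0.11 + 0.117 = 0.227, or +23 points.
- *25 versus 20.* With u₁ = 0.3430, the upper limit is 0.05 + √(0.0930² + 0.0666²) = 0.164, or +16 points.
- *20 versus 20.* With u₁ = 0.2888, the upper limit is √(0.0888² + 0.0666²) = 0.111, or +11 points.

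All three results are non-significant. They leave open excesses of very different size.

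**The case against.** **The test is not the whole safety assessment.** SAP 8.4 and its table list plan AE counts by arm, system organ class and preferred term, tables of related and serious events, narratives, laboratory data and vital signs. Protocol 3.5 and 6.1 add DSMB review. This stands, so it would be wrong to say that safety is answered only by a test. A reader could also compute an interval from the published counts. None of these outputs, however, gives the between-arm difference with its uncertainty.

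**The protocol may already ask for intervals.** Protocol 9.4.2 speaks of estimating the treatment effect with 95% intervals, beneath a list that includes AE/SAE incidence. The wording is ambiguous: it refers to efficacy endpoints and to presentation by arm. The protocol's rule on intervals for categorical data stands under its efficacy heading. The SAP carries neither over to adverse events. If the protocol did intend an interval, that supports adding one.

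**A stronger reading is tempting.** A reader might infer that the sponsor will take non-significance as proof of safety, since Protocol 2.3 says the 10-patient phase 1 study met its safety endpoint with "no remarkable difference in the incidence, frequency, and severity of adverse events between IV Ampion and standard of care". The documents do not support this inference. That sentence is descriptive and reports no test, and nowhere is it said that p>0.05 will be read as showing safety.

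**The miss rate depends on an assumption.** This also stands. Half to three quarters is not a general figure: it needs a placebo SAE rate of about 10% or more and 100 patients per arm.

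**Conclusion.** The point holds as a gap in the planned analysis: the SAP's sole between-arm comparison of AE/SAE incidence yields a p-value with no estimate and no interval. That gap does not depend on any assumed rate. Its practical size does. At 100 per arm and two-sided 0.05, a true 10-point SAE excess goes undetected in about 48% to 74% of trials for assumed placebo rates of 10% to 50%, and in 32% to 41% at a rate of 5%. At 150 per arm the range is about 31% to 61% for rates of 10% to 50%. Even identical observed rates of 20% would leave an excess of up to about 11 points open. It does not follow that the sponsor plans to claim safety from non-significance, or that other safety reviews are missing. This is an inexpensive improvement that should be made before unblinding.

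**What to change.** - In SAP 8.4.1, and in the overall TEAE, related-TEAE and SAE summaries, add the Ampion-minus-placebo risk difference with a two-sided 95% Newcombe interval in the safety analysis set.
- Report the upper limit alongside any p-value that is kept.
- Reconcile the test in 8.4.1 with the statements in SAP 8.1 and 8.6.1 that no statistical testing or analysis is performed.
- Reconcile it also with the hierarchy: Protocol 9.4.2 places AE/SAE incidence first, while SAP 8.6 takes its order from SAP 3.2, which does not list it.

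Intervals for every preferred term are not needed. Nor does this fix require p-values to be made descriptive; that would be part of settling the hierarchy.

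The cost is SAP wording and added columns in a few tables, using data already collected and no extra patients. Settling the hierarchy may also require a change to the protocol. The drawback is a less favourable safety statement, since even equal observed rates would be reported with an upper limit above zero.
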